---

1. **PROTOCOL INFORMATION**

Study Title: To evaluate the preliminary efficacy of our digitally enhanced CHW-led intervention in newly diagnosed PDAC with a pilot randomized controlled trial of 60 PDAC patients comparing the intervention to attention control with usual care

Date: 9/1/2025

Funding Source: DOD/CDRMP

Phase of Study: N/A

Version Date of Protocol: 1.0

3

2. **PRINCIPAL INVESTIGATOR'S INFORMATION**

PI Name, Title: [name], Assistant Professor

Name & Address of Research Institution: Loma Linda University Division of Gastroenterology and Hepatology, [name]

[contact]

Fax #:

Email Address: [[contact]](mailto:[contact])

3. **STUDY PERSONNEL INFORMATION**

Study Staff Name, Title: [name]

[contact]

[contact]

Email Address: [[contact]](mailto:[contact])

Study Staff Name, Title: [name] [name]

[contact]

[contact]

Email Address: [[contact]](mailto:[contact])

4. **STUDY INFORMATION**

Location(s) of Research Activity: Loma Linda University Medical Center

Expected Start/Stop Dates of Research: 07/1/2025 to 07/01/2027

Special Time Sensitivities: Funded through a 2-year grant from the DOD.

Type of Research: Prospective

Anticipated Enrollment number: 60

Patient Population: Patients with pancreatic ductal adenocarcinoma

5. **PURPOSE**

The purpose of this study is to obtain a preliminary estimate of the impact of a community health worker-led intervention by understanding the variance of the primary outcomes (symptom burden and quality of life) using a pilot randomized controlled trial.

## 6. **OBJECTIVES AND PURPOSE**

**Objective:** To evaluate the preliminary efficacy and the variance of primary outcomes (symptom burden and quality of life) of our digitally enhanced CHW-led intervention in newly diagnosed PDAC with a pilot randomized controlled trial of 60 PDAC patients comparing the intervention to attention control with usual care.

- 1 Hypothesis H1: Compared to attention control with usual care the digitally enhanced CHW-led intervention is expected to decrease NCCN-FACT Hepatobiliary-Pancreatic Symptom Index scores and improve HRQoL compared to baseline.

## 7. **STUDY DESIGN**

### a. **Background Information**

Pancreatic Ductal Adenocarcinoma (PDAC) has become the 3rd most common cause of cancer mortality and is projected to become the 2nd largest contributor to cancer mortality by 2030. The overall 5-year survival is 12%, with poor survival (44%) even in patients with local-stage disease.

There are significant racial and ethnic disparities in PDAC, with Non-Hispanic Blacks and Hispanics having lower survival than non-Hispanic whites. These disparities were driven by lower socioeconomic status and delays in receiving chemotherapy, radiotherapy, and germline mutation testing with targeted novel therapies. Hispanics Reasons cited include lack of access to supportive medical care, language barriers, and rural location.

These racial and ethnic disparities in PDAC patients extend to participation in clinical trials, representing the only avenue to improve the prognosis of patients with advanced-stage disease substantially. There is a 53% lower enrollment of Hispanics in clinical trials for PDAC, with no Hispanic patients enrolled among the ten Phase I clinical trials that reported ethnicity. *Patient-reported barriers included mistrust or fear, lack of comfort, information and awareness of the clinical trial process, and, time and resource constraints.* Clinical trials using digital health interventions in PDAC have also been studied to improve healthcare delivery, but Hispanics have the lowest rates of healthcare technology adoption. Reasons for this disparity in Hispanics include lack of access, lack of trust (privacy concerns), lack of comfort with technology, and lack of motivation to use technology to support health. Clearly, Hispanics with PDAC are underrepresented in both therapeutic and digital engagement clinical trials due to cultural, socioeconomic, and information factors, which are addressable.

PDAC patients have low health-related QoL (HRQoL), around the initiation of treatment. For patients receiving palliative chemotherapy, baseline QoL was significantly impaired, and 39% had deterioration in QoL by 3 months and 59% by 6 months. We conducted a prospective cohort study that followed 111 patients with newly diagnosed PDAC. We demonstrated that 72% of patients had a clinically significant decrease in the physical and mental well-being domains of HRQoL at 30 days. In particular, Hispanics with PDAC were found to have significantly lower physical and mental HRQoL than other ethnic groups.

Early initiation of palliative care has been shown to improve HRQoL and overall survival in patients with different solid tumors. Palliative care also increases advanced care planning (ACP) and reduces overall healthcare costs. Regarding PDAC, SEER-based

analyses demonstrated that most palliative care encounters for PDAC occurred near the end of life and were not associated with lower costs. Nevertheless, palliative care encounters within 30 days of diagnosis reduced the number of ED visits, rate of ICU admission, and overall healthcare costs. Multiple clinical trials have demonstrated that early palliative care within 2-4 weeks of diagnosis can improve physical, social, emotional, and functional HRQoL. However, Hispanic PDAC patients are less likely to receive palliative care or hospice referrals than non-Hispanic Whites. Despite evidence that palliative care initiation may benefit PDAC patients, there is limited data on the impact of initiating palliative care at the time of diagnosis in this population.

PDAC patients report critical misconceptions about the treatment of PDAC. They overestimated the effectiveness of aggressive treatments, including surgery. Furthermore, 50% of patients believed that undergoing every possible treatment was the only approach to their disease. Patients with metastatic PDAC expressed that the goal of treatment was improving their survival, and were unsure that palliative care could address symptoms and improve their quality of life. These studies illustrate significant patient misconceptions regarding treatment options, the goal of treatment, and the availability of palliative care.

PDAC is diagnosed with endoscopic ultrasound (EUS)-guided biopsy and delays in establishing care with oncology and palliative care are common. Indeed, one study reported an interval of 26 days from diagnosis to discussing treatment and that there was almost a 2-month delay between the onset of symptoms and treatment initiation. Another study demonstrated a two-week delay from diagnosis to being seen in the oncology clinic and another two-week delay before treatment initiation in the era of neoadjuvant chemotherapy for PDAC. Palliative care has traditionally been delivered after oncologic care initiation, usually late in the course of disease, to patients who are hospitalized units or as a consultative service for patients with uncontrolled symptoms. Since palliative care interventions are typically initiated after establishing care with Oncology, patients' symptom burden and lower QoL are not addressed during these delays in care initiation.

Hispanic patients have very different perspectives than non-Hispanic Whites regarding end-of-life care. Focus groups identified that cultural values of denial, secrecy about prognosis, and a collectivistic, family-centered system influenced Hispanic treatment and hospice decisions, while Non-Hispanic Whites valued more direct discussions. Furthermore, 85% of Hispanic patients with terminal cancer, expressed that their cancer was not terminal and that ACP was unnecessary. They also expressed that communication should involve their family to be effective. Prior studies have not explored the perspectives of Hispanic patients with PDAC. Important cultural differences in approaching terminal cancer and death among Hispanics highlight the need for culturally sensitive patient interventions, including the importance of familial caregivers in communication.

Community health workers (CHWs) are frontline, public health workers who are trusted members of the community served. They bridge the gap between individuals and healthcare systems. Interventions facilitated by CHWs (promotores in Hispanic communities) have improved cancer screening and diagnosis rates, particularly in racial and ethnic minorities. In patients with metastatic cancers receiving treatment, CHW-led interventions focused on ACP reduced acute care costs and improved palliative care engagement. However, this study included a small number of PDAC and Hispanic patients. While CHWs represent a promising workforce for engaging patients, it is unclear if they can address HRQoL and low rates of early palliative care engagement among Hispanic PDAC patients.

**b. Rationale**

**Specific Aim:** To evaluate the preliminary efficacy of our digitally enhanced CHW-led intervention in newly diagnosed PDAC with a pilot randomized controlled trial of 60 PDAC patients comparing the intervention to usual care with attention control.

**Hypothesis H1:** Compared to usual care with attention control, the digitally enhanced CHW-led intervention is expected to decrease NCCN-FACT Hepatobiliary-Pancreatic Symptom Index scores and improve HRQoL compared to baseline.

**c. Endpoints**

The primary endpoint will be change in the symptom burden, measured by the NCCN-FACT Hepatobiliary-Pancreatic Symptom Index and quality of life, measured by the FACT-HEP instrument.

Secondary endpoints include the change in the PCAS-9, ACP Engagement Survey, and ACP completion rates. Other secondary outcomes include direct healthcare costs, ER/urgent care utilization, and response/usage rates to the SMS questions.

**d. Overall study design**

This will be a pilot randomized controlled trial where we will plan on randomizing patients with PDAC in a 1:1 fashion to receive a digitally-enhanced community health worker intervention that will involve visits with the CHW and digital communication to facilitate care navigation and provide early palliative care engagement or usual care with attention control.

**e. Study Procedures and Schedule**

**Recruitment of subjects for the study**

To recruit patients for the interviews, we will screen all of the patients who present for endoscopic ultrasound (with biopsy) to the endoscopy unit or pre-procedure clinic at Loma Linda, as well as patients referred to the medical or surgical oncology clinics with a new diagnosis of pancreatic adenocarcinoma. We will recruit patients from our gastroenterology clinic and endoscopic unit and the oncology clinic (the researcher's patients) both in person and over the phone via a telephone call. We will not contact patients outside our clinical practice but will distribute an IRB-approved flyer with our number to oncology clinics that patients can call and leave a voicemail or email us at our secure HIPAA-complaint Loma Linda email address assigned to our study ([[contact]](mailto:[contact])). We will also distribute an IRB-approved letter to other oncologists informing them of the study so they can distribute the flyer to their patients and inform patients who may be candidates for this study. The reason we are including patients with suspected PDAC is to eliminate delays once they receive a diagnosis as patients previously reported a flurry of medical visits in the 2 weeks after diagnosis. However, patients will need to undergo a biopsy and have pathology confirmation before study initiation. Patients found to have other pathology on biopsy than pancreatic adenocarcinoma will be excluded. We will explain the study in person.

or over the phone when they are referred for a pancreatic biopsy or for oncologic care for a new diagnosis of pancreatic cancer. We will explain that we are recruiting them because they have pancreatic cancer and want to study if a community health worker can help patients like themselves navigate care and engage with palliative care better than the current care that patients receive. If they are interested, they will then be consented using written informed consent at their clinic visit in the clinic or prior to their in-person study visit.

When a patient is diagnosed with PDAC, they receive the diagnosis over the phone and follow-up in clinic. They are referred to medical and surgical oncology and to palliative care for supportive care..

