## 8. **INCLUSION / EXCLUSION CRITERIA**

### **Inclusion criteria:**

- Age 18 to 90
- English or Spanish-Speaking
- Diagnosed with Newly-Diagnosed Pancreatic Adenocarcinoma or has a pancreatic mass on CT/MRI with suspected PDAC and is awaiting biopsy.
- Able to communicate verbally to allow for audio recording to complete an exit-interview
- Must be able to consent

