**Exclusion criteria:**

- Biopsy Does not Confirm Adenocarcinoma of the Pancreas

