**9. RECRUITMENT AND RETENTION**

[name] and the clinical research coordinator (who will be hired and then added to the IRB prior to starting the study) will recruit patients with suspected or newly diagnosed pancreatic cancer from the gastroenterology, oncology and surgical oncology clinics and endoscopy unit (the researcher's patients) No patients outside of the researcher's clinical practice will be contacted regarding the study unless they contact the study investigators first when responding to the study flyer. Pancreatic cancer is diagnosed by endoscopic ultrasound, and patients have a pre-procedure and post-procedure visit where the diagnosis is given and discussed with the patient, and referral to oncology, etc., are made. This is the setting where patients will be included.

Recruitment Method: Study investigators will recruit patients from the endoscopy unit or clinic after a patient is referred with suspected pancreatic cancer or confirmed pancreatic cancer. This method involves recruiting the researcher's own patients.

We will also distribute IRB-approved letters to community oncologists along with an IRB-approved flyer that can be provided to patients which contains a phone number and email that the patient can use to contact the study team. If a patient contacts us expressing interest, then we will recruit them over the phone and then enroll them in the study after obtaining consent.

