## **12. POTENTIAL RISKS**

- Anxiety or stress related to talking about pancreatic adenocarcinoma.
- Loss of confidentiality.

To mitigate the risk of anxiety and stress, we will let patients guide the conversation with the CHWs so that they can redirect the conversation and what resources they want based on their anxiety/stress level or if some topic is difficult for them to talk about. We also will have their palliative care provider engage with them if they experience any anxiety or stress.

To mitigate the loss of confidentiality, we will de-identify all study documents except the informed consent document (which will be stored either electronically in LLEAP or in a secure locked drawer in the office of [name]). We will use a unique patient ID number on all other study documents. All protected health information collected will be securely stored in an encrypted LLU computer and will not be shared with anyone electronically. Any paper records will be stored in the same locked drawer in [name] office at LLU.

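### The stated reason for recruitment, that the patient has pancreatic cancer, is also given to patients still awaiting biopsy, whom the protocol itself classes as suspected cases

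*Protocol*

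**What the plan says.** Under Recruitment of subjects for the study (Protocol section 7.e), the study is explained in person "or over the phone when they are referred for a pancreatic biopsy or for oncologic care for a new diagnosis of pancreatic cancer". The next sentence gives the content of that explanation, without separating the two routes: "We will explain that we are recruiting them because they have pancreatic cancer". It goes on to say that the study asks whether a community health worker can help with navigating care and engaging with palliative care.

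The same subsection says that approaching suspected cases is intended: "The reason we are including patients with suspected PDAC is to eliminate delays once they receive a diagnosis". It requires pathology confirmation before the study starts for a patient, and adds: "Patients found to have other pathology on biopsy than pancreatic adenocarcinoma will be excluded".

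Section 8 agrees. A patient qualifies who "has a pancreatic mass on CT/MRI with suspected PDAC and is awaiting biopsy", and the only exclusion criterion is "Biopsy Does not Confirm Adenocarcinoma of the Pancreas". Section 9 again names both suspected and confirmed cases as the people to be recruited. Section 12 lists two risks, the first being "Anxiety or stress related to talking about pancreatic adenocarcinoma".

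**The concern.** The explanation states as fact something that, for one of the two groups receiving it, is not yet known. A patient referred for biopsy has a finding on imaging and a suspicion. The protocol expects some of these patients to turn out not to have the study disease, because it has a criterion to remove them.

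What is at stake is patient protection and the accuracy of what is said before consent. Followed as written, the study team would give a patient an unverified cancer diagnosis as the reason for the invitation, possibly by telephone, before pathology is available. Some of those patients would later learn that the statement was wrong. The coordinator who will share the recruiting has yet to be hired (section 9) and will rely on the protocol text, which does not tell that person to distinguish the two groups.

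**Working it through.** The point rests on no effect size, error rate or sample size, so the check is to set the statements side by side.

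| Question | What the protocol says | Where |
|---|---|---|
| When is the study explained? | At referral for biopsy, or at referral for oncologic care after a new diagnosis | 7.e, Recruitment |
| What reason is given? | That the patient has pancreatic cancer, for both routes | 7.e, Recruitment |
| Are unconfirmed patients approached on purpose? | Yes, to avoid delay after diagnosis | 7.e, Recruitment; section 9 |
| Is a confirmed diagnosis needed to meet the inclusion criteria? | No, a mass on imaging with biopsy pending is enough | Section 8, inclusion |
| What if biopsy does not confirm? | The patient is excluded | 7.e, Recruitment; section 8, exclusion |
| Is there other wording for suspected cases? | None found | Whole protocol |

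**Step 1: order of events.** Rows 1 and 3 put the explanation before pathology for the biopsy-referral route. Section 10 (Informed Consent Process) fits this: the study is explained at first contact, which may be in the endoscopy unit, and consent follows.

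**Step 2: truth of the statement at that moment.** Row 4 means that the diagnosis is open for these patients, so the statement in row 2 is unverified for all of them.

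**Step 3: truth afterwards.** Row 5 means that the protocol foresees patients without confirmed adenocarcinoma. For those with no cancer the statement is false. For any with a different malignancy it is inaccurate about the disease under study.

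**Step 4: could another provision correct it?** The rule on pathology confirmation governs when the study starts for a patient, not what is said on approach. Section 9 describes visits around the procedure, where "patients have a pre-procedure and post-procedure visit where the diagnosis is given and discussed with the patient", but a visit before the biopsy cannot convey its result.

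**Size.** To reach *m* confirmed patients by the pre-biopsy route when a share *q* of biopsies does not confirm PDAC, *m*/(1 − *q*) patients must be approached, and *m*/(1 − *q*) − *m* of them would have been told something not borne out. The documents give neither *m* nor *q*. They give only the planned total of 60, so *m* could in principle lie anywhere from 0 to 60. No figure is reported, and the point does not need one.

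**The case against.** The best defence is that this is loose drafting. The sentence summarises a conversation and is not a verbatim script. The documents mention an IRB-approved flyer and letter, but those texts and the consent form are not in the material at hand and may be worded correctly. The same paragraph speaks openly of suspected disease and of confirmation by pathology, so the authors plainly know the difference. The investigator shares in recruitment, and section 11 (Screening) ties screening to chart review for a clinical visit, so a cold telephone call from a coordinator is the worst case and not the typical one.

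Much of this stands. It makes the harmful reading less likely to be carried out. It does not remove the contradiction: the protocol is the controlling text, it allows telephone contact, and it prescribes one reason for two groups of which only one fits.

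A reader might infer three stronger points that the documents do not support:

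- **That distress is the trial's main risk and that this sentence causes it.** Section 12 lists two risks without ranking them. That the statement provokes distress is a reasonable inference but not something the protocol states.
- **That baseline scores are distorted.** Section 7.e (Study Intervention) does put baseline surveys at enrolment. But pathology must be confirmed before the study starts, and the presurvey in the CHW intervention outline falls within 7 days of diagnosis, so patients surveyed on that timing already have a diagnosis. Patients not confirmed are excluded. The recruitment explanation is the same whichever arm a patient is later assigned to. No bias between arms follows.
- **That the safeguards in section 12 must be extended to patients excluded after biopsy.** Community health worker or palliative care contact for people outside the trial would be a new procedure, and a wording contradiction does not call for it.

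**Conclusion.** The point holds as an internal contradiction with a consequence for patients. The recruitment explanation in section 7.e conflicts with the inclusion of suspected cases (sections 7.e, 8 and 9) and with the exclusion of those not confirmed (sections 7.e and 8). As written, every patient approached before biopsy would be told before consent that they have a cancer that has not been established, and for some this would be untrue. It may cause the anxiety that section 12 names.

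The textual mismatch is certain. How many patients it touches is unknown, and the conclusion assumes that staff follow the protocol sentence and that the unseen recruitment materials do not already correct it. It changes no endpoint, allocation or analysis. It should still be corrected before any patient awaiting biopsy is approached, because the statement concerns a cancer diagnosis and the correction is almost free.

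**What to change.** Reconcile the recruitment paragraph of section 7.e with sections 8 and 9 by giving two explanations:

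- **Patients awaiting biopsy:** they are approached because a finding in the pancreas is being evaluated for suspected cancer, and they can take part only if pathology confirms PDAC.
- **Patients with a confirmed diagnosis that has already been disclosed to them:** the present explanation.

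Check that the flyer, the letter to oncologists, any telephone wording and the consent form draw the same distinction.

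The cost is a wording amendment and its IRB review. No patients, visits, staff or procedures are added, and the design and analysis stay as they are.

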### **Study Intervention**

Usual Care consists as follows:

An attention control where patients are provided handouts from PANCAN and videos from the NPF and study staff contact them monthly over video to administer the surveys for the outcomes but also answer any questions.

After a PDAC diagnosis is made, referrals are made to Medical and Surgical Oncology and Palliative Care, and the patient follows up in the Gastroenterology clinic to discuss the diagnosis and related symptoms. Baseline surveys will be completed at the time of enrollment in both the usual care and CHW-led intervention arms.

The CHW-led intervention arm will receive the same care/referrals as usual care but in addition work with a CHW as follows:

The study visits will take place in person in the clinic, School of Behavioral Health conference room, or the patient's home or virtually using Microsoft Zoom (depending on the patient's preference).

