## Diagram of pancreatic cancer patients' intervention

### Use of Digital Applications

Patients will be provided access to web-based educational modules through Docola and Youtube that provide general information about pancreatic cancer, palliative care, and treatment options.

In between the study visits, the patients will receive the Edmonton Symptom Assessment Scale via Twillio-RedCap SMS once a week (an integrated short message system platform in Loma Linda's implementation of RedCap). A positive ESAS is defined as three symptoms with  $> 7/10$  scores. If the CHW receives a positive ESAS, they will call the patient to ask how they are doing and then forward the responses to the Palliative care team, which will triage the patient as needed clinically to respond to these symptoms. The CHW will also ask the patient if they have questions or concerns twice a week using Twillio-RedCap SMS messages.

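### The recruitment explanation signals the favoured arm and describes the comparator as current care only, an avoidable expectation cue in a trial with visible allocation and self-reported outcomes

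*Protocol*

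**What the plan says.** In section 7.e, under Recruitment of subjects for the study, the protocol sets out what staff will explain to patients they approach: that the study asks if a CHW can help them "navigate care and engage with palliative care better than the current care that patients receive". The sentence does not mention the other arm's materials or contacts.

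The comparator is defined more fully elsewhere. Section 6, section 7.b and section 7.d all call it usual care together with an attention control. Section 7.e, Study Intervention, gives the content: "An attention control where patients are provided handouts from PANCAN and videos from the NPF and study staff contact them monthly over video", and the purpose of that contact is "to administer the surveys for the outcomes but also answer any questions". The intervention arm "will receive the same care/referrals as usual care but in addition work with a CHW as follows".

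On outcomes, section 7.c states: "The primary endpoint will be change in the symptom burden, measured by the NCCN-FACT Hepatobiliary-Pancreatic Symptom Index and quality of life", the latter by FACT-HEP. The secondary endpoints include PCAS-9 and the ACP Engagement Survey. Section 17 lists all four instruments as surveys given to patients.

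**The concern.** A patient in this trial cannot fail to notice whether a CHW has been assigned, and the protocol describes no blinding. When the outcome is the patient's own rating, what the patient was led to expect can affect the rating. The recruitment explanation supplies such an expectation. It presents the CHW as the thing that may improve on ordinary care and gives no sign that the other arm also receives something added for the study. A patient then assigned to that arm may conclude that they received nothing new.

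An attention control is normally included to balance non-specific influences between arms. A recruitment message that leaves it out and points to the other arm works against that aim. At stake is the preliminary estimate of effect, which the protocol gives as its purpose (sections 5 and 6) and which will inform the case for a larger trial. The tests and model contrasts in section 18 cannot separate expectation from effect.

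**Working it through.** The protocol states no figure on this point, so the main check sets the sections side by side.

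**Comparator**
- Recruitment explanation (7.e): the care that patients currently receive.
- Sections 6, 7.b and 7.d: usual care plus attention control.
- Study Intervention (7.e): handouts, videos, and monthly staff video contact that also answers questions.

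The explanation omits the attention-control part altogether. It is incomplete against four other places in the same document.

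**What the explanation cues**
- It names navigating care and engaging with palliative care.
- The outcomes nearest to that are PCAS-9 and the ACP Engagement Survey, both secondary and self-reported. The cue is direct there.
- The primary scores (symptom index, FACT-Hep) are not mentioned. The cue is indirect there.

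**Illustration of sensitivity**

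Inputs from the protocol: 60 patients (section 4), allocated 1:1 (section 7.d), so n = 30 per arm; two-sample t-test (section 18). Assumed, because the protocol does not give them: two-sided 5% level, no true effect, and a differential reporting shift of b SD between arms.

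- Standard error of the difference: √(2/30) = 0.258 SD.
- 95% half-width, 58 degrees of freedom: 2.002 × 0.258 = 0.517 SD.
- Noncentrality: b / 0.258 = b × √15.
- Rejection probability from the noncentral t:

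| Assumed shift b (SD) | Noncentrality | Rejection, 30 per arm | Rejection, 20 per arm |
|---|---|---|---|
| 0 | 0 | 5.0% | 5.0% |
| 0.1 | 0.387 | 6.7% | 6.1% |
| 0.2 | 0.775 | 11.9% | 9.5% |
| 0.3 | 1.162 | 20.8% | 15.2% |

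The 20-per-arm column assumes one third of patients are lost; the protocol gives no dropout rate. The noncentrality column is for 30 per arm.

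The estimated difference moves by b itself. A uniform shift within an arm leaves that arm's SD unchanged, so the SD that section 18 carries forward to later power calculations would not be affected.

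The table shows what a shift of a given size would do. It does not show that the wording causes one. The relevant quantity is the increment over what visible allocation already produces, and nothing in the document allows that to be estimated.

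**The case against.** The strongest case against has four parts.

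First, the sentence poses an open question: staff want to study if the CHW helps. Some statement of the study question is needed for consent. This stands in part. Consent requires that both arms be disclosed, but it does not require one to be framed as possibly better than what patients get now.

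Second, the text summarises an explanation and is not a verbatim script. Section 10 says the study is explained with its risks and benefits and that questions are answered. The flyer, the letter and the consent form are not available to this review and may describe both arms evenly. This stands: those documents can be checked for the same wording, but it cannot be said that they share it.

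Third, a reader might infer that the wording defeats the attention control. The protocol does not support that. Control patients still receive the handouts, videos and monthly contact whatever they were told at recruitment, and an attention control does not conceal the study question. Unequal contact is a separate matter: monthly in one arm, while in the other "The CHW will also ask the patient if they have questions or concerns twice a week using Twillio-RedCap SMS messages".

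Fourth, a reader might infer that the primary results will be biased, in a known direction, towards the CHW arm. That also goes too far. Only a risk can be shown. Withdrawal by disappointed controls, for example, need not favour the CHW arm: if those with the worst scores leave, the remaining controls look better.

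**Conclusion.** The point holds as a minor one. The recruitment explanation describes the comparator incompletely against sections 6, 7.b, 7.d and the Study Intervention text, and it signals which arm is favoured. Because patients will know their arm and rate their own outcomes, this adds an avoidable risk of expectation or disappointment bias. The risk is most direct for PCAS-9 and the ACP Engagement Survey and indirect for the symptom index and FACT-Hep.

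The size is unknown. The 0.1 to 0.3 SD range is an assumption, as is the 5% level. Even 0.3 SD is smaller than the 0.517 SD half-width of the trial's own 95% interval at full enrolment. In a pilot the consequence would be a distorted preliminary effect estimate, not a false confirmatory claim. Some bias of this kind will remain under any wording, because allocation stays visible.

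**What to change.** Reword the recruitment explanation in section 7.e so that it describes both arms neutrally. For example: the study compares two forms of support for people with suspected or confirmed pancreatic cancer, one with a community health worker and text messages, the other with educational materials and monthly contact from study staff, and it is not known whether one is better. Delete the clause that compares the CHW with current care. Saying suspected or confirmed also fits section 8, which admits patients still awaiting biopsy. Check the flyer, the letter to oncologists and the consent form for the same framing, and change them only if they have it.

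The cost is IRB approval of the revised text. Both arms are described at least as fully as before, so consent is not weakened. The change reduces the risk but does not remove it.
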